Institution/Department : Kaohsiung Veterans General Hospital

Principal Investigator (PI) : [name]

Research Project Title : Comparing the efficacy and impact on gastrointestinal microbiome of reverse hybrid therapy and bismuth quadruple therapy in *Helicobacter pylori* eradication

NCT Number : NCT02547038

Date of the document : 01 02 2019 (MM/DD/YYYY)

ABSTRACT

Background: With the rising prevalence of antimicrobial resistance, the failure rate of the standard triple therapy has declined to unacceptable level (<80%) worldwide. A 14-day hybrid therapy invented by our study group appears very promising in *H. pylori* eradication, achieving excellent eradication rates of 99% and 97% according to per-protocol and intention-to-treat analyses, respectively. Recently, we demonstrated that the eradication rate of reverse hybrid therapy was higher than that of standard triple therapy. However, whether reverse hybrid therapy achieves a higher eradication rate than bismuth quadruple therapy remained unanswered.

Aims: The aims of this randomized controlled trial are (1) to compare the efficacies of reverse hybrid therapy and bismuth quadruple therapy, (2) to investigate the host and bacterial factors predicting the treatment outcomes of the two eradication regimens.

Methods: Consecutive 352 *H. pylori*-infected subjects are randomly assigned to receive either a 14-day reverse hybrid therapy or a 14-day bismuth quadruple therapy. On recruitment, blood sampling for genotyping of *CYP2C19* is carried out, and antibiotic susceptibility of *H pylori* strains will be checked. Subjects are asked to return at the end of the 2nd week to assess drug compliance and adverse events. *H pylori* status will be re-assessed at week 6 after the end of anti-*H. pylori* therapy. Finally, the rates of eradication, adverse events and compliance will be compared between groups by chi-square test, and the host and bacterial factors influencing each efficacy of the regimen are assessed by multivariate analysis.

Introduction

Helicobacter pylori (*H. pylori*) infection is the principal cause of chronic gastritis, gastric ulcer,

duodenal ulcer, gastric adenocarcinoma and gastric mucosa-associated lymphoid tissue lymphoma.¹

In most international guidelines,²⁻⁴ 14-day standard triple therapy is still recommended as a choice

of treatment for the first-line therapy of *H. pylori* infection, especially in areas of low

clarithromycin resistance ($\leq 15\%$). However, the eradication rates of standard triple therapy have declined to less than 80% in most countries because of the rising prevalence of clarithromycin resistance.⁵ Several strategies including bismuth-containing quadruple therapy and non-bismuth-containing quadruple therapy have therefore been proposed to increase the eradication rate.^{5,6}

In the Maastricht V/Florence Consensus Report,³ bismuth quadruple therapy is the treatment of choice for the first-line therapy of *H. pylori* infection in areas of high clarithromycin resistance ($> 15\%$) and an alternative in areas of low clarithromycin resistance. In the recent American College of Gastroenterology (ACG) guideline, it is also recommended as a first-line treatment for *H. pylori* infection.⁴ However, the complicated administration of bismuth quadruple therapy easily reduces the adherence of patients, and the complex therapy is associated with a high frequency of adverse events.^{7,8}

Hybrid therapy developed by Hsu et al. in 2011 consists of a dual therapy with a proton pump inhibitor (PPI) and amoxicillin for 7 days followed by a quadruple regimen with a PPI, amoxicillin, clarithromycin and metronidazole for 7 days.⁶ It achieved an eradication rate of 97.4% by intention-to-treat (ITT) analysis and 99.1% by per-protocol (PP) analysis in Taiwan.⁶ Subsequent randomized controlled trials demonstrated that 14-day hybrid therapies were comparable or more effective than 10-day sequential therapies.^{9,10} A recent large multicentre randomized controlled trial documented that 14-day hybrid and 14-day concomitant therapies had comparable efficacy in the treatment of *H. pylori* infection, and both could cure more than 90% of patients with *H. pylori* infections in areas of high clarithromycin and metronidazole resistance.¹¹ Currently, it is a recommended first-line

treatment choice in the ACG guideline⁴ and the Taiwan *Helicobacter pylori* Consensus Report.¹²

However, hybrid therapy requires additional two antibiotics in the last 7 days, which can confuse patients and may dampen enthusiasm for its use. Reversing the sequence of drug administration (a quadruple regimen followed by a dual regimen) can simplify hybrid therapy. The aims of this randomized controlled trial are (1) to compare the efficacies of reverse hybrid therapy and bismuth quadruple therapy, (2) to investigate the host and bacterial factors predicting the treatment outcomes of the two eradication regimens.

PATIENTS & METHODS

Study population

The open-labeled trial is conducted at the Kaohsiung Veterans General Hospital and Kaohsiung Medical University Hospital in Taiwan in accordance with the principles of good clinical practice from the Declaration of Helsinki. The study protocol will be approved by the Ethics Committees of the Kaohsiung Veterans General Hospital and the Kaohsiung Medical University Hospital. All patients give written informed consent before participating in the study.

We will recruit 352 patients to the study if they meet the following criteria: they are adult patients aged ≥ 20 years and have *H pylori* infection. The exclusion criteria include The exclusion criteria include (1) previous *H pylori*-eradication therapy, (2) patient with allergic history to the medications used, (3) patients with previous gastric surgery, (4) coexistence of serious concomitant illness (for example, decompensated liver cirrhosis, uremia), and (5) pregnant

women.

Randomization and treatment

This is a randomized controlled trial. Eligible *H. pylori*-infected subjects are randomly assigned to a 14-day reverse hybrid therapy (a 7-day quadruple regimen with pantoprazole 40 mg twice daily, amoxicillin 1 g twice daily, clarithromycin 500 mg twice daily, and metronidazole 500 mg twice daily, followed by a 7-day dual regimen with pantoprazole 40 mg twice daily and amoxicillin 1 g twice daily) or a 14-day bismuth quadruple therapy (pantoprazole 40 mg twice daily, bismuth tripotassium dicitrate 120 mg, and tetracycline 500 mg four times daily for 14 days). All drugs are taken one hour before breakfast and dinner. Patients with peptic ulcers in initial endoscopy receive an additional 4-week pantoprazole therapy (40 mg orally once daily), while patients with symptomatic gastritis only take additional four-weeks of antacid.

On recruitment, patients are requested to complete a standard record for a complete medical history and demographic data. Additionally, blood sampling for genotyping of *CYP2C19* is carried out. To assess eradication efficacy and status of ulcer healing, repeated endoscopy with rapid urease test, histological examination and culture is performed for peptic ulcer patients at the sixth week after the end of anti- *H. pylori* therapy. Urea breath test is conducted to assess *H. pylori* status in the subjects with gastritis and in peptic ulcer subjects who refuse follow-up endoscopy,. Eradication is defined as (1) negative results of both rapid urease test and histology, or (2) a negative result of urea breath test.

Finally, the eradication rates by both intention-to-treat and per-protocol analyses, adverse events and compliance will be compared between groups by chi-square test, and the host and bacterial factors influencing the efficacy of eradication therapy are assessed by multivariate analysis.

Statistical analysis

The primary outcome variable is eradication rate. The secondary outcome variables are the rate of adverse events and compliance. Chi-square test with or without Yates correction for continuity and Fisher's exact test are used when appropriate to compare the major outcomes between groups using the SPSS program (version 10.1, Chicago, Illinois, USA). A *P* value less than 0.05 is considered statistically significant.

Eradication rates are evaluated by ITT and per-protocol (PP) analyses. ITT analysis includes all randomized patients who have taken at least one dose of study medication. Patients whose infection status is unknown following treatment are considered treatment failures for the purposes of ITT analysis. The PP analysis excludes the patients with unknown *H. pylori* status following therapy and those with major protocol violations.

To determine the independent factors affecting the treatment response, Host and bacterial parameters are analyzed by univariate analysis. These variables include the following: age (<60 or \geq 60 years), gender, history of smoking, history of alcohol consumption (<80 g/day or \geq 80 g/day), ingestion of coffee (<1 cup/day or \geq 1 cup/day), ingestion of tea ((<1 cup/day or \geq 1 cup/day), coexistence of a systemic disease (yes or no), previous history of peptic ulcer disease, endoscopic appearance (ulcer or gastritis), CYP2C19 polymorphism, drug compliance (good or poor), and antibiotic susceptibility. Those variables found to be significant by univariate analysis are subsequently assessed by a stepwise logistic regression method to identify independent factors for eradication outcome.

REFERENCES

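### The search for predictors of eradication leaves out hospital, so a hospital difference that does not act through a listed factor could be reported as an independent host or bacterial factor

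*Combined protocol and SAP*

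**What the plan says.** The Study population section names two recruiting hospitals ("The open-labeled trial is conducted at the Kaohsiung Veterans General Hospital and Kaohsiung Medical University Hospital in Taiwan") and gives the total but not the split: "We will recruit 352 patients to the study if they meet the following criteria". The Randomization and treatment section says only that "Eligible *H. pylori*-infected subjects are randomly assigned to a 14-day reverse hybrid therapy" or to the bismuth regimen. It does not mention stratification by hospital.

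For the comparison of arms, the Statistical analysis section states: "Chi-square test with or without Yates correction for continuity and Fisher's exact test are used when appropriate to compare the major outcomes between groups". The threshold follows: "A *P* value less than 0.05 is considered statistically significant".

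The last part of that section covers Aim 2. It introduces host and bacterial parameters with "These variables include the following: age" and ends with "CYP2C19 polymorphism, drug compliance (good or poor), and antibiotic susceptibility". Between these come gender, smoking, alcohol, coffee, tea, systemic disease, ulcer history and endoscopic appearance, which makes twelve variables in all. Only those significant on univariate analysis go into a stepwise logistic regression, and the survivors are to be called independent factors. Hospital does not appear in any part of the analysis text.

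**The concern.** Treatment is randomised, but age, ulcer status, CYP2C19 type and the other listed factors are not. A comparison of eradication between patients with and without such a factor can therefore be confounded by anything linked to both the factor and the outcome. Hospital is an obvious candidate. Case mix may differ between the two sites, and so may the apparent failure rate.

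The plan itself offers one route. Patients with unknown post-treatment status count as failures in the intention-to-treat analysis, so poorer follow-up at one hospital raises its failure rate with no biological cause. A listed factor that is more common at that hospital would then be associated with failure. A model without hospital can remove this only so far as other listed factors carry the hospital difference. At stake is one of the trial's two aims: a difference in site conduct could be published as a patient or bacterial predictor.

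**Working it through.** The plan has no figure on hospital effects to reproduce.

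**Inputs from the documents:** two hospitals, 352 patients, significance at 0.05.

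**Assumed inputs:** 352/2 = 176 patients per hospital; failure rates qA and qB; factor prevalences fA and fB; no effect of the factor within either hospital.

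**Step 1: the spurious difference.** With equal hospitals, the crude failure rates with and without the factor are

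- r1 = (fA·qA + fB·qB)/(fA + fB)
- r0 = [(1−fA)·qA + (1−fB)·qB]/(2 − fA − fB)

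For failure 5% v 15% and prevalence 30% v 60%:

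- r1 = (0.30×0.05 + 0.60×0.15)/0.90 = 0.105/0.90 = 11.67%
- r0 = (0.70×0.05 + 0.40×0.15)/1.10 = 0.095/1.10 = 8.64%

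The factor does nothing, yet the crude difference is 3.03 points.

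**Step 2: how often the screen flags it.** The pooled failure rate is 0.10, n1 = 176×0.90 = 158.4 and n0 = 176×1.10 = 193.6.

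- SE = √[0.10×0.90×(1/158.4 + 1/193.6)] = 0.0321
- z = 0.0303/0.0321 = 0.943
- P(Z > 1.96 − 0.943) + P(Z < −1.96 − 0.943) = 0.155 + 0.002 = about 15.6%

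The same formula for other settings, beside simulation of the uncorrected chi-square test (40,000 or more trials per setting; two values are from separate runs):

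| Failure by hospital | Prevalence by hospital | Crude difference (points) | Formula | Simulation |
|---|---|---|---|---|
| 5% v 10% | 30% v 40% | 0.55 | 5.4% | 5.4%, 5.6% |
| 5% v 15% | 30% v 40% | 1.10 | 6.2% | 6.4%, 6.6% |
| 6% v 12% | 30% v 60% | 1.82 | 9.1% | 9.4% |
| 5% v 15% | 30% v 60% | 3.03 | 15.6% | 15.9% |
| 5% v 15% | 20% v 70% | 5.05 | 34.9% | 34.7% |

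Stratified by hospital (Mantel-Haenszel), the simulated rate is about 5% throughout. These rates are for the univariate screen. A flagged factor must also survive the stepwise stage, but that stage never sees hospital.

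**Step 3: both gaps are needed.** If qA = qB, or if fA = fB, then r1 = r0 and the rate returns to about 5%.

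**Step 4: which hospital differences remain.** Differences in resistance or adherence act through antibiotic susceptibility and compliance, and both are listed. Incomplete follow-up is not represented by any listed variable. It counts as failure under intention to treat and is excluded per protocol. The plan does not say which set the predictor analysis uses, so this route is open only if the intention-to-treat outcome is taken.

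**Step 5: the comparison of arms.** With 176 per arm and half of the patients at each hospital, the chance imbalance in hospital share has SD √(2×0.25/176) = 5.3 points. A 10-point hospital difference therefore shifts the arm difference by about 0.10×5.3 = 0.5 point per SD, and this is random, not systematic. In simulation with allocation at 50:50 within each hospital, the unstratified test kept an error rate of 4.9% to 5.1% even with hospitals 15 points apart. Power for an assumed 8-point difference, unstratified v stratified, was 76.1% v 76.0%, 78.8% v 78.8% and 67.8% v 68.7% in three settings.

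**The case against.** The strongest reply is that the harm rests on inputs the documents do not supply. Neither the failure rate nor the case mix by hospital is given, and with modest gaps the inflation almost vanishes. With the Yates correction, which the plan permits, the modest settings give only 3.4% to 4.4%. This stands, and it limits how strongly the point can be put.

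Second, susceptibility and compliance are already candidates. If a hospital difference works through them, reporting them is a correct finding. This also stands and narrows the point to residual differences.

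Third, the list is introduced with wording that need not be exhaustive. This does not help: the list is of host and bacterial parameters, and hospital is neither.

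Fourth, twelve independent tests at 0.05 already carry a 1 − 0.95^12 = 46% chance of at least one false positive without any hospital effect. That is true and is a larger problem in the modest settings, but adjusting for hospital addresses a different error.

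Fifth, failures may be few. If eradication were 90% to 95% (an assumption), 352 patients would give 352×0.05 = 18 to 352×0.10 = 35 failures. Models fitted by regimen, as the Abstract can be read to intend, would have about half as many. This is a real cost, though of one term only.

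A reader might also infer that leaving hospital out biases the primary comparison, or that the planned chi-square test must be replaced. The documents do not support this. Patients are randomised, and nothing indicates that the allocation ratio differs between hospitals; with a common ratio the unstratified test is valid and loses almost no power.

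**Conclusion.** The point holds for the predictor analysis of Aim 2 only. As written, that analysis cannot separate a residual hospital difference from an effect of a listed factor. The consequence is a possibility, not a demonstrated error. It needs the hospitals to differ in both failure rate and factor prevalence, by a path outside the listed variables.

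Under the assumed gaps and an equal split of patients, the false-positive rate for one null factor ranges from about 6% (modest) through about 16% (large) to about 35% (very large), against about 5% with stratification. Nothing in the documents says where in that range the trial lies. This is a cheap improvement worth making, and not a threat to the primary result.

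**What to change.** In the predictor paragraph of the Statistical analysis section:

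- adjust each univariate screen for hospital, for example with a Mantel-Haenszel test or a logistic model with a hospital term;
- keep hospital as a forced term in the logistic model, outside the stepwise selection;
- state which analysis set supplies the outcome, since this decides whether missing follow-up counts as failure there;
- report eradication by arm within each hospital, descriptively.

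The planned comparison of arms can stay as it is. A hospital-stratified Mantel-Haenszel test is at most an optional sensitivity analysis.

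The cost is SAP wording and one degree of freedom in a model that may have few failures. The recruiting hospital should already be on record for every patient, so no new data or procedures are needed.

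### The control arm is named a quadruple therapy but lists three drugs, and its four-times-daily dosing conflicts with a rule that places all drugs before breakfast and dinner

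*Combined protocol and SAP*

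**What the plan says.** The first aim, given in the Abstract and again at the end of the Introduction, is "to compare the efficacies of reverse hybrid therapy and bismuth quadruple therapy". The primary outcome is the eradication rate, compared between the two arms.

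The control arm is defined once, in PATIENTS & METHODS, Randomization and treatment: "14-day bismuth quadruple therapy (pantoprazole 40 mg twice daily, bismuth tripotassium dicitrate 120 mg, and tetracycline 500 mg four times daily for 14 days". The experimental arm is set out earlier in the same sentence and begins with "a 7-day quadruple regimen with pantoprazole 40 mg twice daily, amoxicillin 1 g twice daily, clarithromycin 500 mg twice daily, and metronidazole 500 mg twice" a day. The next sentence gives the timing for the whole trial: "All drugs are taken one hour before breakfast and dinner".

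The Abstract, Introduction and Statistical analysis section refer to the control regimen by name only. None of them lists its components, frequencies or timing.

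**The concern.** There are two contradictions in the only text that defines the comparator.

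- **Components.** The name implies four drugs and the list has three.
- **Schedule.** Tetracycline, and possibly bismuth, is ordered four times daily, while the timing sentence puts every drug at two points in the day.

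If sites follow the text as written, control patients receive a three-drug regimen, possibly on half the stated occasions. An advantage for reverse hybrid therapy could then not be read as an advantage over bismuth quadruple therapy, which is the question the trial sets out to answer.

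Other planned elements rest on the same paragraph:

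- Compliance is a secondary outcome and also a good/poor covariate in the analysis of factors affecting eradication. It needs a prescribed dose count.
- The per-protocol set excludes major protocol violations. A patient cannot obey both sentences.
- The exclusion for allergy to the study medications needs a complete drug list. So does the choice of which susceptibility results matter for the control arm.

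The Introduction makes the complicated administration of bismuth quadruple therapy, and the poorer adherence it causes, part of the case against this comparator. The schedule is therefore part of what is being compared.

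**Working it through.** The check is mainly a count. The plan has no figure of its own to reproduce here. The total of 352 is given without assumed rates, power or allocation ratio, and the point does not depend on it.

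**1. Drugs named in Randomization and treatment**

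| Regimen | Drugs named | Count |
|---|---|---|
| Reverse hybrid, days 1–7 (called quadruple) | pantoprazole, amoxicillin, clarithromycin, metronidazole | 4 |
| Reverse hybrid, days 8–14 (called dual) | pantoprazole, amoxicillin | 2 |
| Control, days 1–14 (called quadruple) | pantoprazole, bismuth, tetracycline | 3 |

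In the experimental arm the label matches the count in both phases (4 and 2). The Introduction likewise uses quadruple for four named drugs when it describes hybrid therapy. By the protocol's own usage, the control list is 4 − 3 = 1 short of its name.

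As background only, the title of reference 7, which the Introduction cites when discussing bismuth quadruple therapy, names "a capsule containing bismuth subcitrate potassium, metronidazole, and tetracycline given with omeprazole". That is 3 + 1 = 4 drugs. A reference title does not define this trial's regimen, and the count above does not need it.

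**2. Dosing occasions in the control arm**

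The inputs are "bismuth tripotassium dicitrate 120 mg, and tetracycline 500 mg four times daily for 14 days" and the timing sentence.

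| | Four-times-daily clause | Breakfast-and-dinner sentence |
|---|---|---|
| Occasions per day | 4 | 2 |
| Tetracycline doses over 14 days | 4 × 14 = 56 | 2 × 14 = 28 |
| Tetracycline per day at 500 mg per occasion | 4 × 500 = 2000 mg | 2 × 500 = 1000 mg |
| Bismuth per day at 120 mg per occasion | 4 × 120 = 480 mg, if the clause covers bismuth | 2 × 120 = 240 mg |

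The gap is two-fold. The wording leaves open whether the four-times-daily phrase reaches back to bismuth, so the bismuth frequency is ambiguous even before the timing sentence is considered. Pantoprazole and every reverse hybrid drug are twice daily, so the timing sentence does not conflict with them.

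**3. Illustration for compliance**

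The plan gives no compliance formula. If compliance were doses taken divided by doses prescribed, a patient who followed the timing sentence exactly would score 28 / 56 = 50% for tetracycline against the four-times-daily line. A patient who followed the four-times-daily line would take 56 / 28 = 2 times the count implied by the timing sentence.

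**4. Patients affected**

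The plan states "We will recruit 352 patients to the study". With 1:1 allocation, which is an assumption, the control arm has 352 / 2 = 176 patients.

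**5. Is it an artefact of the text?**

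There is no blackout mark, gap or broken table at this point. The drug list is grammatically complete, with its conjunction before the last item.

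**The case against.** The strongest reply is that this is a drafting slip. One item missing from the list, plus a timing sentence written with the twice-daily arm in mind, would produce exactly this text. Other slips are visible: the exclusion criteria open with a repeated phrase, and the Abstract says a failure rate has declined where the context calls for a success rate. Sites may have had correct instructions, and the documents do not show what was dispensed.

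Further objections concern reach:

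- The timing sentence does not contain the word *only*.
- The schedule conflict does not change who enters the intention-to-treat set or how eradication is scored. Its direct analytic effect is on compliance and the per-protocol set.
- The 50% figure assumes a dose-count definition that the plan does not give, and it concerns tetracycline alone.
- A reference title cannot define the control arm.

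Most of this stands as a limit on what can be claimed. Mis-treatment is not shown, the 50% figure is an illustration, and the reference title is background. None of it removes the contradiction. An instruction for all drugs that names two occasions and makes no exception cannot be reconciled with four occasions, with or without the word *only*. If the cause is a drafting slip, the correction is simply cheaper. It remains necessary because no other text supplies the comparator's components or timing.

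**Conclusion.** The concern holds. As written, the control arm is one drug short of its name and carries two incompatible schedules, 56 against 28 tetracycline doses over 14 days, with the bismuth frequency unclear as well. The whole control arm is affected, about 176 of 352 patients under an assumed 1:1 split.

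Confidence in the textual conflict is high. The effect on eradication rates cannot be sized from the documents, since it depends on what sites actually gave. The point must still be fixed, because this paragraph is the sole definition of the comparator for the primary outcome, and compliance and the per-protocol exclusions rest on it too.

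**What to change.** Reconcile four items in Randomization and treatment so that they describe one complete control regimen: the arm's name, its component list, the frequency of each component (bismuth included), and the timing sentence that covers all drugs. Which regimen and schedule are intended is for the sponsor to state.

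Then compute compliance, and judge major protocol violations, against that reconciled schedule. Check that site instructions and dispensing records at both hospitals agree with it. If they show that patients received something other than the reconciled text, report what was given.

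The cost is a wording correction or short amendment plus the records check. The sample size and the analysis method need not change for this point.

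### The only planned comparison of eradication between arms is unadjusted; prespecifying a covariate-adjusted risk difference would add modest precision at almost no cost

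*Combined protocol and SAP*

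**What the plan says.** The primary endpoint is binary: "The primary outcome variable is eradication rate". The closing paragraph of the section Randomization and treatment gives the comparison: "Finally, the eradication rates by both intention-to-treat and per-protocol analyses, adverse events and compliance will be compared between groups by chi-square test". Statistical analysis adds the variants: "Chi-square test with or without Yates correction for continuity and Fisher's exact test are used when appropriate to compare the major outcomes between groups". It sets the threshold: "A *P* value less than 0.05 is considered statistically significant". No adjusted or stratified arm effect, risk difference or confidence interval is mentioned.

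Randomization and treatment says that subjects are assigned at random and describes no stratification.

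Baseline factors appear only in the last paragraph of Statistical analysis. Host and bacterial variables, including "endoscopic appearance (ulcer or gastritis"), CYP2C19, age and susceptibility, are screened one at a time, and the significant ones go into a stepwise logistic regression. Treatment arm is not in that list; drug compliance is.

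Endoscopic appearance also has a role in the conduct of the trial. "Patients with peptic ulcers in initial endoscopy receive an additional 4-week pantoprazole therapy", while gastritis patients take antacid for the same period. At week 6 ulcer patients have repeat endoscopy with biopsy-based tests. "Urea breath test is conducted to assess" gastritis patients, and also ulcer patients who decline endoscopy.

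**The concern.** The trial collects, at or before the start of treatment, several variables that could be related to eradication, but the arm comparison uses none of them. Endoscopic appearance is the clearest candidate. It is known at the initial endoscopy, and the two groups it defines differ in aftercare and, by default, in how eradication is measured. Stratifying or adjusting for it follows from the plan's own design.

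Two things are at stake. The first is precision: adjusting for a prognostic baseline variable reduces the variance of the arm difference. The second is prespecification. If the arms turn out unbalanced on some factor, someone will ask for an adjusted result. As written, the only model available is one whose variables are chosen by their significance in the trial data, that may include compliance (observed after randomisation), and that is not stated to contain treatment arm. In an open-label trial, it is better to fix the adjusted analysis before results are seen.

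**Working it through.** The plan gives no figure on this point to reproduce. It gives no power, effect size, margin or dropout behind the 352 patients ("We will recruit 352 patients to the study if they meet the following criteria"), no prevalence or effect for any factor, and no eradication rate for bismuth quadruple therapy. All sizes below are therefore illustrative.

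**Inputs.** N = 352 and α = 0.05 are from the document. Assumed: 1:1 allocation (176 per arm), a two-sided test, ulcer share 25–50%, and eradication of 92% v 92%, 88% v 95% or 90% v 97.4%. The 97.4% is the Introduction's intention-to-treat figure for hybrid, not reverse hybrid, therapy.

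**1. Validity of the crude test.** Simulation used one binary factor (prevalence 20% or 50%; odds ratio 2, 4 or 8), 92% eradication in both arms and 40,000 trials per setting. Type I error was 4.9–5.1% for the crude chi-square and 4.8–4.9% for a Cochran-Mantel-Haenszel (CMH) test. Mean crude and stratified differences agreed to within 0.0001.

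**2. Size of chance imbalance.** The standard deviation (SD) of the arm difference in ulcer share is √(2p(1−p)/176).
- p = 0.25: √(0.375/176) = 0.046
- p = 0.35: √(0.455/176) = 0.051
- p = 0.50: √(0.500/176) = 0.053

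A gap of 10 points or more then arises in about 3%, 5% and 6% of trials. The shift in the eradication difference is the gap times the difference in eradication between strata: 0.10 × 5 = 0.5 points, or 0.10 × 10 = 1.0 point. The standard error of the crude difference at 92% is √(2 × 0.92 × 0.08/176) = 0.029, or 2.9 points. Even a rare gap moves the result by about a third of a standard error or less.

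**3. Stratifying on one factor** (prevalence 20%; gains at 50% are similar or smaller).

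| Eradication | Odds ratio | SD crude | SD stratified | Power crude | Power CMH |
|---|---|---|---|---|---|
| 88% v 95% | 2 | 0.0293 | 0.0292 | 66.6% | 66.6% |
| 88% v 95% | 4 | 0.0294 | 0.0290 | 66.3% | 67.5% |
| 88% v 95% | 8 | 0.0296 | 0.0282 | 66.8% | 70.9% |
| 90% v 97.4% | 2 | 0.0255 | 0.0255 | 84.0% | 84.3% |
| 90% v 97.4% | 4 | 0.0255 | 0.0253 | 84.1% | 85.2% |
| 90% v 97.4% | 8 | 0.0257 | 0.0248 | 84.1% | 86.7% |

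**4. Adjusting for endoscopic appearance, CYP2C19 group and age** (logistic regression standardised to a risk difference). Ratios of adjusted to crude variance from two sets of simulations with assumed effects:
- no predictive effect: about 1.01
- odds ratio 1.5: 0.998–1.003
- odds ratio 2: 0.993–1.001 in one set, 0.985–0.994 in the other
- odds ratio 3: 0.976–0.979 in one set
- odds ratios 3–4: 0.92–0.97 in the other set

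No bias was seen.

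**5. Conversion to power.** For a variance cut v, new power ≈ Φ(z/√(1−v) − 1.96), with z = 1.96 + Φ⁻¹(crude power). At 67% crude power, z = 1.96 + 0.44 = 2.40.
- v = 0.02: Φ(2.424 − 1.96) ≈ 0.679, a gain of about 0.9 points
- v = 0.05: Φ(2.462 − 1.96) ≈ 0.692, about 2.2 points
- v = 0.08: Φ(2.502 − 1.96) ≈ 0.706, about 3.6 points

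**6. Failures available to a model.** At 95% and 90% overall eradication, 352 × 0.05 ≈ 18 and 352 × 0.10 ≈ 35. At the hybrid figures, one arm of 176 would have 176 × 0.026 ≈ 4.6 failures (97.4%) or 176 × 0.009 ≈ 1.6 (99.1%, per protocol). In the last case the chance of none is 0.991^176 ≈ 0.20, and the logistic arm coefficient would then have no finite estimate.

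**The case against.** The case for leaving the plan alone is good. An unadjusted chi-square on a randomised binary endpoint is conventional and valid, and its standard error already allows for chance imbalance. The gain is small and, with weak predictors, nil. With few failures a logistic model can break down where Fisher's exact test does not. All of this stands. It limits the size of the point and shapes the fix, but does not supply the missing adjusted analysis.

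Four stronger readings are tempting and are not supported.
- A reader might infer that imbalance biases the primary result. It does not on average, and step 2 shows how little one realised gap would move it.
- A reader might infer that endoscopic appearance wholly determines the outcome test and is the most important factor. Ulcer patients who decline endoscopy have the breath test, the rules are the same in both arms, and the document gives no effect of ulcer status on eradication and no difference in test accuracy.
- A reader might infer that the sponsor expects these factors to drive eradication. The second aim is to investigate them; no expectation is stated for any.
- A reader might infer a sizeable saving in patients. Variance cuts of up to 10% appeared in simulation only with strong predictors and with antibiotic resistance and its interaction with arm in the model, which is not the model proposed here.

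**Conclusion.** The point holds as a modest matter of efficiency and prespecification, not as a flaw that threatens the primary result. The crude comparison is the only one planned between arms, and the predictor regression does not stand in for an adjusted arm effect. Adjusting for three baseline factors would lower the variance by about 0–2% if odds ratios are at most 2, and by about 3–8% at odds ratios of 3–4 (one set of simulations gave just over 2% at 3). The power gain is mostly 0 to 2 points and reaches about 3.5 only at the 8% end. These sizes rest on 1:1 allocation and on assumed prevalences, effects and eradication rates. That the crude test is valid, and that the plan contains no adjusted arm effect, does not depend on those assumptions.

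**What to change.** In Statistical analysis, prespecify an eradication risk difference between arms with a 95% confidence interval, from a logistic regression standardised to a risk difference. Include treatment arm, endoscopic appearance, CYP2C19 metaboliser group and age (continuous). State that these covariates are fixed in advance and not chosen by univariate significance, that drug compliance is excluded, and how a missing genotype is handled. As a minimum, use a Cochran-Mantel-Haenszel test stratified by endoscopic appearance.

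Report the crude chi-square or Fisher result alongside. State that the stratified or Fisher result is used if an arm has too few failures for the logistic model, and give the rule for deciding this before results are seen. Keep the stepwise regression for the second aim only.

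The cost is some SAP wording and a few lines of code, with no new data. The downside is a limit of about three covariates, because failures will be few, and no gain if the chosen factors prove unrelated to eradication.
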